**Aim 1: Determine if Total30 Sphere CLs provide a comfortable wearing experience all day.**

Hypothesis 1: Patients who are refit in Total30 Sphere CLs will have a comfortable wearing experience after 16 hours as based on visual analog scale (VAS) scores.

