**6. Subject Compliance & Daily Comfort:** All subjects will be encouraged to wear their CLs for at least 16 hours per day and to start wearing their CLs between 6:00 AM and 8:00 AM on days that they will be completing text messaging surveys. Subjects will be educated that they will be required to complete Qualtrics surveys on their phone. Subjects will be asked to complete a test survey before they leave the first study visit to make sure that their system is compatible with their phone. These surveys will ask subjects about their eye comfort with a visual analog scale (slider scale with 0 as neutral comfort, -50 extremely uncomfortable, and +50 extremely comfortable) at before CL application, directly after CL application, and at 8 hours, 10 hours, 12 hours, 14 hours, and 16 hours post lens application on the first 5 days. This same system will be used to monitor how many hours they wear their CLs each day. Subjects will finally be asked to complete these surveys on day 14 and 1 day prior to their 1-month visit (1 month) to understand comfort over the life of the CLs. Subjects will be called the day before the day 14 and 1-month surveys to remind them about these surveys. Subjects will be allowed to schedule their day 14 and 1-month surveys within 3 days of these time points to allow for better compliance.

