## Data Analysis

All data will be analyzed with Stata/IC 15 (StataCorp LLC; TX, USA). VAS comfort scores will serve as the primary endpoint and be reported as percent of patients who are comfortable at each timepoint. Comfort comparisons across visits or across the wear day will serve as exploratory endpoints, and these outcomes will be measured with paired t-tests or ANOVA.

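### Aim 1 asks about comfort all day, but separate percentages at each survey time only bound the share of wearers comfortable throughout a day

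*Combined protocol and SAP*

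**What the plan says.** The Specific Aim section has one aim: "Determine if Total30 Sphere CLs provide a comfortable wearing experience all day". The hypothesis under it is narrower: wearers "will have a comfortable wearing experience after 16 hours as based on visual analog scale (VAS) scores".

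Visit 1, item 6 (Subject Compliance & Daily Comfort) sets the surveys "at before CL application, directly after CL application, and at 8 hours, 10 hours, 12 hours, 14 hours, and 16 hours post lens application". That is seven surveys a day, six of them after the lens goes on. They are completed on the first 5 days, and "Subjects will finally be asked to complete these surveys on day 14 and 1 day prior to their 1-month visit", so there are seven survey days. The response is a "slider scale with 0 as neutral comfort, -50 extremely uncomfortable, and +50 extremely comfortable".

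Data Analysis makes the comfort score the primary endpoint and summarises it one way: "VAS comfort scores will serve as the primary endpoint and be reported as percent of patients who are comfortable at each timepoint". It adds that "Comfort comparisons across visits or across the wear day will serve as exploratory endpoints", using paired t-tests or ANOVA. No section defines an outcome for one subject over one whole day, or says how the separate percentages combine to answer Aim 1. The plan also does not single out one timepoint or one survey day as the main result.

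**The concern.** A natural reading of all-day comfort is that a given wearer is comfortable from application to the end of the day. That is a statement about one person's set of scores. A percentage at each timepoint is a statement about a group at one moment. The same series of percentages can come from one stable group who are always comfortable, or from many wearers who each have an uncomfortable spell at a different time.

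What is at stake is interpretation. Under an aim worded as all-day comfort, a run of high percentages invites the conclusion that the same share of wearers were comfortable all day. The true share is never higher than the lowest of those percentages and may be well below it. The Conclusions section intends the data for patient education, where that difference matters.

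**Working it through.** **Inputs from the documents.** There are six surveys per day after lens application: directly after, and at 8, 10, 12, 14 and 16 hours (Visit 1, item 6). The base sample is 40 subjects, plus 8 for attrition and missing data, giving 48 (Sample Size). The plan gives no figure for an all-day share, so there is none to reproduce.

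**Assumed inputs.** The documents give no comfort rates and no within-subject correlations. Those used below are illustrations.

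**Step 1: what the separate percentages allow.** If p_k is the proportion comfortable at survey k, the proportion comfortable at all six lies between max(0, 1 − Σ(1 − p_k)) and min(p_k).

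- Every survey at 90%: lower bound 1 − 6 × 0.10 = 0.40, upper bound 0.90. With 40 subjects, 4 are uncomfortable at each survey. If they are always the same four, 36 of 40 are comfortable throughout. If they are always different, 40 − 24 = 16 of 40 are.
- Percentages declining as 98, 97, 95, 93, 90, 85: the shortfalls sum to 0.02 + 0.03 + 0.05 + 0.07 + 0.10 + 0.15 = 0.42. The lower bound is therefore 0.58 and the upper bound 0.85.

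**Step 2: values between the bounds.** Repeated scores on one person are correlated, so the lower bounds are extreme. I assumed normally distributed latent scores with a common correlation ρ. With t_k = Φ⁻¹(p_k), the proportion comfortable at all six is

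∫ φ(u) ∏ Φ((t_k − √ρ·u)/√(1 − ρ)) du.

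| Assumed percentages | ρ = 0.5 | ρ = 0.7 | ρ = 0.9 | 16-hour percentage |
|---|---|---|---|---|
| 90% at every survey | 68% | 74% | 82% | 90% |
| 98, 97, 95, 93, 90, 85% | 74% | 78% | 83% | 85% |

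The gap to the 16-hour percentage is about 8 to 22 points in the flat case and about 2 to 11 points in the declining case.

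**Step 3: when the gap is zero.** The all-day share equals the 16-hour percentage if everyone comfortable at 16 hours was also comfortable at each earlier survey. Comfort that only falls within each wearer satisfies this. Discomfort on application that later settles, or scores that move back and forth across the cut-off, does not. The plan does not say which is expected and has no summary that would show it.

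**The case against.** The strongest reply is that Hypothesis 1 is the plan's own testable version of Aim 1, and it concerns comfort after 16 hours. Once a cut-off is set, the 16-hour percentage answers it directly. That stands. A reader might infer that the trial fails to report what it set out to test, and the documents do not support that. The gap is with the wording of Aim 1, not with Hypothesis 1.

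Second, much of the protocol describes the goal as mapping comfort over the day (Introduction, Sample Size, Publication Plans, Conclusions), and a series of percentages suits that purpose. This also stands. It is a reason to keep the series, but the series does not provide the per-wearer figure.

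Third, the flat 90% example is unfavourable. The Introduction says discomfort increases towards the end of the wear day, and a declining pattern shrinks the gap. A reader might take the 40% lower bound as a likely result. It would require every uncomfortable spell to fall on a different wearer, which is implausible for repeated scores on the same people.

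Fourth, a reader might infer that the within-subject data go unused. They do not: the exploratory paired comparisons use them. Those comparisons contrast comfort between times, however, and do not give the share comfortable throughout.

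**Conclusion.** The point holds in a limited form. The planned percentages answer Hypothesis 1 at 16 hours. For all-day comfort as Aim 1 words it, they give an upper bound and a weak lower bound, and not the share itself. The likely size is modest. Under the declining pattern, which fits the Introduction better, the all-day share is about 2 to 11 points below the 16-hour percentage. It is zero points below if comfort only falls within each wearer. These sizes rest on assumed rates, assumed correlations of 0.5 to 0.9 and a common-correlation model. The bounds rest on arithmetic alone.

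This is a change to consider. The study is a descriptive pilot with no stated success threshold, so no error rate, sample size or decision is affected. What is affected is what may be claimed from the result.

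**What to change.** Keep the percentages at each timepoint, and state that the 16-hour percentage answers Hypothesis 1. Then add a per-subject summary to Data Analysis:

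- **Definition.** Report the percent of subjects whose answered scores after application and at 8, 10, 12, 14 and 16 hours are all on the comfortable side of the cut-off, with an exact 95% interval. Use the same cut-off as for the percentages at each time. The documents do not state one, so it must be written down first.
- **One main day.** Name one of the seven survey days in advance as the main all-day result, and report the others as supporting.
- **Incomplete days.** Any failing answered score counts as not comfortable throughout. Subjects with no failing score but a missed survey, or a survey answered after lens removal, are shown as a best-case/worst-case range.
- **Wear window.** Reconcile the 16-hour survey in Visit 1, item 6 with the Subjects section. The latter allows a start at 8:00 AM and asks for wear until 11:00 PM, which is 15 hours.
- **Wording.** Describe the result as comfortable at all surveyed times, because there is no survey between application and 8 hours. Do not describe the percentages at each time as the share comfortable all day.

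The cost is a paragraph of analysis text and one derived variable, with no new data or visits. The headline figure will be somewhat less favourable, and its precision is that of a small study: 28 of 40 (70%), for example, has an exact 95% interval of about 53% to 83%.

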## Training of Study Personnel

Prior to enrolling any subjects all examiners will participate in a training session developed by [name], OD, PhD. This full investigator meeting will ensure that all study investigators are performing the procedures in the same manner. Data from each investigator's first subject will also be monitored for quality control by the study's coordinator before the investigator is allowed to see additional subjects.

## IV. Study Timeline

	2021	2021	2021	2021	2021	2021
	July	Aug	Sep	Oct	Nov	Dec
Activity						
Contracting						
IRB Preparation						
Data Collection						
Data Analysis						
Final Study Report						

## V. Publication Plans

An abstract describing comfort across the wear day will be submitted to Academy 2022 San Diego (main outcome), and an abstract will be submitted to Heart of America Eye Congress describing how comfort changes over the wear month. A manuscript on the same topics will be submitted to *Contact Lens & Anterior Eye* after the Academy 2022 San Diego abstract is submitted because the Academy requires that abstract materials have not been presented/submitted elsewhere.

## VI. Conclusions

This project will be among the first to describe the progression of CL comfort throughout the day for Total30 Sphere CLs. These data are important because they could provide insight into end of day CL discomfort, and they will provide data needed for proper patient education.

